4. INVESTIGATIONAL PLAN

4.1. Overall Study Design and Plan

DMID Protocol 18-0011 follows a Phase I randomized, double blind study design enrolling males and non-pregnant females aged 18-45 years of age, inclusive, who are in good health as determined by medical history and physical examination, and meet all eligibility criteria, including erythrocyte sedimentation rate (ESR) and negative urine or serum pregnancy test (for females). This clinical trial is designed to assess the safety, reactogenicity and immunogenicity of either the 2018/2019 Fluzone or Flublok Quadrivalent Influenza Vaccines (QIV), manufactured by Sanofi Pasteur (SP) given without adjuvant or with one of two adjuvant formulations, AF03 (SP) or Advax-CpG55.2 (Vaxine Pty Ltd).

In this trial, subjects will be stratified by prior receipt of licensed, seasonal influenza vaccine (defined as receipt of at least one of the 2017/2018 and/or 2018/2019 influenza vaccines) and will be randomly assigned to 1 of 6 study arms to receive a single dose of one of the two seasonal 2018/2019 QIV vaccine formulations with or without one of the two adjuvants (Day 1). On approximately Day 90, each subject will receive a single dose of the seasonal 2019/2020 influenza vaccine. Treatment will be assigned to each study arm as described in [Table 1](#).

To determine early safety signals for this Phase I study, enrollment will proceed in a staged fashion for the first 6 sentinel subjects. The first six subjects will be randomized and vaccinated with one each from Groups 1-6. These six subjects will be followed through Day 8. If any of the pre-specified halting rules for the sentinel subjects occur, the study will be halted and reviewed by the DSMB. If no pre-specified safety signals are encountered enrollment will proceed.

The DSMB will review the data when the 8-day reactogenicity and clinical safety laboratory data following the first study vaccination are available for 50% of study subjects. Enrollment will not be paused for this review. An additional scheduled DSMB review will occur when all HAI, NAI and Neut data for Day 1, and Day 29 and safety data through Day 57 following the first study vaccination, are available.

Reactogenicity will be measured by the occurrence of solicited injection site and systemic reactions from the time of the first study vaccination through Day 8. Unsolicited non-serious adverse events (AEs) will be collected from Day 1 through approximately Day 29. Serious adverse events (SAEs); Adverse Events of Special Interest (AESIs) including reports of tearing, dry mouth, dry eyes; medically-attended adverse events (MAAEs), new-onset chronic medical conditions (NOCMCs); and potentially immune-mediated medical conditions (PIMMCs), will be collected Day 1 through approximately 12 months after the first study vaccination. Clinical safety laboratory evaluations (hematology and chemistry) will be performed at screening, immediately prior to the first study vaccination, and at approximately Day 8.

Immunogenicity testing will include performing serological assays to assess hemagglutination inhibition (HAI), neutralizing (Neut), and neuraminidase inhibition (NAI) titers at multiple time points following both study vaccinations. Antibody responses will be determined for both influenza vaccine strains and heterologous influenza strains. Additional exploratory immunologic responses will include longitudinal assessments of the kinetics, magnitude, specificity, and/or quality of influenza-specific memory B cells, plasmablasts, circulating T follicular helper (TFH) cells, and non-neutralizing antibody responses to HA and NA antigens (Multiplex ELISA, NA ELISA, Systems Serology).

4.2. Discussion of Study Design, Including the Choice of Control Groups

This study uses a dose comparison concurrent control design. All subjects receive the same study product (2018/2019 Fluzone or Flublok QIV) with or without adjuvants on Day 1. On Day 90, all subjects receive the seasonal vaccine of either Fluzone 2019/2020 QIV or Flublok 2019/2020 QIV.

4.3. Selection of Study Population

The study population for this clinical trial is 240 males and non-pregnant females, 18-45 years old, who are in good health and meet all eligibility criteria. The subjects will be recruited from the general population at the participating Vaccine Trial and Evaluation Unit (VTEU) sites that have substantial experience conducting large influenza vaccine studies.

4.4. Treatments

4.4.1. Treatments Administered

2018/2019 Flublok QIV, 2018/2019 Fluzone QIV, 2019/2020 Flublok QIV, 2019/2020 Fluzone QIV, AF03 adjuvant, and Advax-CpG55.2 adjuvant will be administered.

4.4.2. Identity of Investigational Product(s)

See the study protocol for details of study product formulation.

4.4.3. Method of Assigning Subjects to Study Arms (Randomization)

Enrollment/randomization will be performed through the enrollment module in the electronic data capture system maintained by the Statistical and Data Coordinating Center (SDCC).

Eligible subjects will be stratified by clinical site and prior receipt of licensed, seasonal influenza vaccine (defined as receipt of at least one of the 2017/2018 and/or 2018/2019 influenza vaccines) and randomly assigned with allocation (1:1:1:1:1:1) to one of 6 study arms indicated in [Table 1](#). The treatment sequence was generated using permuted block randomization to provide an approximately balanced allocation to the study arms during the study.

4.4.4. Selection of Doses in the Study

Each subject will receive a dose of either 2018/2019 Fluzone QIV or 2018/2019 Flublok QIV on Day 1 and a dose of 2019/2020 Fluzone QIV or 2019/2020 Flublok QIV on approximately day 90.

- 2018/2019 and 2019/2020 Flublok QIVs are formulated to contain 180 µg of HA per 0.5 mL dose, with 45 µg of HA derived from each of four influenza virus strains recommended for the 2018/2019.
- 2018/2019 and 2019/2020 Fluzone QIVs are formulated to contain 60 µg of HA per 0.5 mL dose with 15 µg of HA from each of the four influenza virus strains.
- Each 0.25mL dose of AF03 that will be administered admixed with vaccine contains approximately 12.5 mg of squalene
- Each Advax-CpG55.2 adjuvant will be made of two components Advax (delta inulin) and CpG55.2. Each 2.0 mL vial contains 0.5 mL of a 50 mg/mL suspension of delta inulin in phosphate buffered saline and 0.5 mL of a 2 mg/mL solution of CpG55.2.

4.4.5. Selection and Timing of Dose for Each Subject

Each subject is to be randomly assigned to a study group which will define the type and dose of 2018/2019 QIV and adjuvant that they will receive. The first vaccination takes place on the day of randomization. On approximately Day 90 after the first vaccination (protocol defined window of Day 90 +/- 14 days post first vaccination), each subject will receive a single dose of the seasonal 2019/2020 influenza vaccine. This dosing interval was selected so receipt of the 2019/2020 dose would fall within the recommended timeframe for season vaccination.

4.4.6. Blinding

This trial is double-blinded; subjects, investigators, study personnel performing any study-related assessments following study vaccine administration, and laboratory personnel performing antibody assays are blinded to dosage within study vaccination schedule.

The randomization scheme was generated by the SDCC and provided to unblinded study personnel (i.e., pharmacists performing study vaccination preparations and unblinded study vaccine administrators) at the participating VTEU sites who will not be involved in study-related assessments or have subject contact for data collection following study vaccine administration.

The Data and Safety Monitoring Board (DSMB) may receive data in aggregate and presented by group. The DSMB may also be provided with expected and observed rates of the expected AEs in an unblinded fashion and may request treatment assignment be unblinded for an individual subject if required for safety assessment. The DSMB will review grouped and unblinded data in the closed session only.

4.4.7. Prior and Concomitant Therapy

Administration of any medications, therapies, or vaccines (including prescription and over-the-counter drugs as well as herbals, vitamins, and supplements) from 60 days prior to study vaccination through 21 days post final vaccination will be solicited from the participant during screening, enrollment, and follow-up. Any reported prior therapies from up to 30 days prior to vaccination through 28 days post first study vaccination will be recorded in the appropriate data collection form.

Use of concomitant medications is allowed prior to and during the trial with the exception of medications and therapies that might interfere with the evaluation of the investigational product. Medications in this category include the prohibited medication per the Subject Exclusion Criteria (protocol Section 5.1.2). In addition, the site principal investigator or appropriate sub-investigator may identify other medications that should not be used due to a risk to subject safety or assessment of reactogenicity and immunogenicity.

4.4.8. Treatment Compliance

All subjects were to receive two doses of study product administered in the clinic.

4.5. Efficacy (Immunogenicity) and Safety Variables

See [Table 2](#) for schedule of study procedures.

4.5.1. Safety Variables

Safety will be assessed by the frequency and severity of:

1. SAEs occurring from the time of the first study vaccination through approximately 12 months after the first study vaccination.
2. Solicited AEs – reactogenicity events occurring from the time of study vaccination through approximately Day 8 after the first study vaccination.
 - a. Injection site reactions including pruritus, ecchymosis, erythema, induration/swelling, edema, pain, and tenderness.
 - b. Systemic reactions including fever, feverishness, fatigue, malaise, myalgia, arthralgia, headache, and nausea.
3. Clinical safety laboratory AEs occurring from the time of the first study vaccination through approximately Day 8 after the first study vaccination. Parameters to be evaluated include white blood cells (WBC), hemoglobin (Hgb), platelets (PLT), alanine aminotransferase (ALT), total bilirubin (T. Bili), aspartate aminotransferase (AST), gamma-glutamyl transferase (GGT), alkaline phosphatase (ALP) serum lipase and serum amylase and creatinine (Cr).
4. Unsolicited AEs – non-serious AEs occurring from the time of the first study vaccination through approximately Day 29 after the first study vaccination.
5. All protocol specified AESIs, MAAEs, NOCMCs and PIMMCs, from the time of the first study vaccination through approximately 12 months following the first.

Grading scales for injection site and systemic solicited reactions, vital signs, and clinical laboratory parameters are provided in [Table 7](#), [Table 8](#), [Table 9](#), and [Table 10](#).

4.5.2. Immunogenicity Variables

Individual HAI assay results against the 2018/2019 QIV strains, 2019/2020 QIV strains, and heterologous H3 influenza strains (A/Kenya/105/2017 [H3N2], A/Louisiana/13/2017 [H3N2], A/Aksaray/4048/2016 [H3N2], A/Shandonglaicheng/1763/2016 [H3N2], and A/Michigan/84/2016 [H3N2]) will be performed at Q2 Solution laboratory under the responsibility of GCI and results will be reported by GCI.

Individual Neut assay results will be performed and reported by Global Clinical Immunology (GCI) lab at Sanofi Pasteur laboratory for the 2018/2019 QIV strains, 2019/2020 QIV strains, and heterologous H3 influenza strains (A/Kenya/105/2017 [H3N2], A/Louisiana/13/2017 [H3N2], A/Aksaray/4048/2016 [H3N2], A/Shandonglaicheng/1763/2016 [H3N2], and A/Michigan/84/2016 [H3N2]).

Individual NAI results against the 2019/2020 QIV strains, 2018/2019 QIV strains, and heterologous N1 and N2 NA antigens (A/OMAN/5532/2017, A/CAMEROON/9766/2017, A/Human/Hubei/3/2005, A/LOUISIANA/13/2017, A/TOWNSVILLE/51/2016, A/AKSARAY/4048/2016) will be performed by Q2 Solution laboratory under the responsibility of GCI and the data will be reported by GCI.

HAI, NAI, and Neut assay results are reported as a reciprocal titer with values of 10×2^k , where $k=0, 1, 2$, etc. The lower limit of detection for the HAI, NAI and Neut assays is 1:10; values below the limit of detection are reported as '<10', and for analysis are imputed as one-half the limit of detection ($10/2 = 5$). The upper limit of quantitation (ULOQ) varies by assay and strain. Values above the upper limit of quantitation will be reported as ' \geq ULOQ', and for analysis are imputed as the upper limit of quantitation (ULOQ). HAI, NAI, and Neut

assays will be done in duplicates. Both titers will be reported for the HAI and NAI assays, but only one Geometric Mean Titer (GMT) will be reported for Neut assay. For analysis of HAI and NAI, the geometric mean (calculated on natural log scale) of repeated results for each sample will be computed and used as the response for all subsequent calculations. The variation arising from multiple measurements for an individual at a single time point is not used in subsequent calculations. See Section 3.2 for definitions of derived variables for the analysis of HAI, NAI, and Neut data.

Influenza-specific IgG, IgM, and IgA memory B cells using Multiplex FluoroSpot assay will be performed by Caprion Biosciences Inc. These assay results are reported as Spot Forming Cells (SCF) per million PBMC. Two or three replicated will be reported.

Influenza specific plasmablasts using multiparametric flow cytometry will be reported by SP-VaxDesign. The results will be measured in "Arbitrary Units/ml" against serum standard curve. One or two replicates will be provided.

Influenza specific Tfh cells using multiparametric flow cytometry will be reported by SP-VaxDesign. Percent Tfh and number of Tfh will be reported, and one or two replicates will be provided.

Functional non-neutralizing Fc-effector results will be reported by SeromYx Inc.

Assay results for quantification of HA binding antibodies against different influenza H3 strains obtained by Antibody Forensic Technology using multiplex ELISA and NA binding antibodies against different influenza NA antigens from ELISA will be reported by Sanofi Pasteur FluNXT Immunology laboratory. No repeats will be performed; one result will be reported.

All immunogenicity data will be uploaded into the SDCC's electronic data capture system.

5. SAMPLE SIZE CONSIDERATIONS

This study is planned to enroll a total of 40 subjects in each group. This study is not designed to test a formal null hypothesis. Rather, it is intended to obtain sufficient data to obtain meaningful estimates of the immune response and to uncover any safety issues that occur at a sufficiently high rate that they might be observed in a study of this size. As such, the type one error rate, $\alpha = 0.05$, is not adjusted for multiple comparisons. While this study is not designed to test any specific null hypothesis, the following tables illustrate the precision and power that is available for select estimates and comparisons of interest.

[Table 3](#) indicates the probability of observing one or more safety events, such as solicited injection site or systemic reactogenicity events or an unsolicited non-serious AE of a particular type for sentinel subjects (N=4 or 6), for a single adjuvanted/ unadjuvanted study arm/stratum (N = 40 or 60), for all subjects receiving the same seasonal QIV (N= 120), for all subjects in the trial (N=240).

Binomial confidence intervals (CI) are widest (have the least precision) when the response rate is 50%.

[Table 4](#) is presented to indicate the worst-case scenario for precision of observed exact (Clopper-Pearson) binomial confidence intervals.

[Table 5](#) illustrates the minimum detectable differences in the proportion of subjects responding (e.g., attaining seroconversion or a titer $\geq 1:40$) between two adjuvanted study arms using a two-sided Likelihood Ratio Test and $\alpha = 0.05$.

6. GENERAL STATISTICAL CONSIDERATIONS

6.1. General Principles

Unless otherwise specified, all continuous variables will be summarized using the following descriptive statistics: n (non-missing sample size), mean, standard deviation, median, maximum and minimum. The frequency and percentages (based on the non-missing sample size) of observed levels will be reported for all categorical measures. In general, all data will be listed, sorted by treatment and subject, and when appropriate by visit number within subject. All summary tables will be structured with a column for each study arm in the following order:

- Group 1: Fluzone
- Group 2: Fluzone + AF03
- Group 3: Fluzone + Advax-CpG
- Group 4: Flublok
- Group 5: Flublok + AF03
- Group 6: Flublok + Advax-CpG

All tables will be annotated with the total population size relevant to that table/treatment, including any missing observations.

6.2. Timing of Analyses

6.2.1. Expedited Report

Clinical, safety, and reactogenicity data through approximately 56 days after study vaccination will represent the interim clinical database for this trial. Once the last subject completes the visit that occurs approximately 56 days after first study vaccination, the interim clinical database will be cleaned, monitored, and locked. Upon receipt of immunogenicity data for Day 1 and Day 29 (HAI, NAI, and Neut against 2018/2019 QIV strains and heterologous strains) and safety data through Day 57, the sponsor will authorize the SDCC to transfer to Sanofi Pasteur a copy of this unblinded data set. An Expedited Report containing analyses of safety data through Day 57 and HAI, NAI, and Neut data for 2018/2019 QIV strains from baseline (Day 1) and Day 29 unblinded by study arm only will be prepared by the SDCC. These analyses may be made available to the sponsor and pharmaceutical partners for planning subsequent trials as well as to the DSMB for review.

The analyses performed for the Expedited Report or using the data set provided to Sanofi Pasteur will not be used to make any decisions concerning the conduct of this trial. As it is anticipated that subjects will remain in long term safety follow-up at the time of these analyses, blinded investigators and DMID medical monitors not involved in the analysis, publication, or Expedited Report preparation will be responsible for assessing SAEs and AESIs (including Protocol Specified AESIs, MAAEs, NOCMCs and PIMMCs) until all subjects have completed the final follow-up visit.

Tables to be included in the Expedited Report are indicated with the symbol * in the title in [Appendix 1](#).

6.2.2. Clinical Study Report

The final CSR will be completed after the last subject's last visit is completed, and the final clinical database including all long-term safety follow-up data is cleaned, monitored and locked, and all primary and secondary immunogenicity data are available. After such data are reported in the database and the data are considered clean and complete, a "topline" subset of the immunogenicity tables planned for the CSR will be provided to DMID and Sanofi Pasteur. These tables are indicated with a [¥] symbol after the title in the appendix.

Analysis of exploratory immunogenicity endpoints may be performed and released as the data are available from the research laboratory. Any such analyses would be considered the final analysis for the endpoint and included in the CSR. Additional exploratory immunogenicity endpoint data not available at the time of CSR preparation may be included in an addendum to the CSR, manuscript(s), or other report.

6.3. Analysis Populations

6.3.1. Safety Population

The Safety Analysis population includes all subjects who received the first study vaccination. For all safety analyses subjects will be grouped based on actual vaccination(s) received.

6.3.2. Modified Intention-to-Treat (mITT) Population

The modified intent-to-treat (mITT) population includes all randomized subjects who received the first study vaccination and contributed at least one post-first study vaccination venous blood samples for immunogenicity testing (HAI, NAI or Neut antibody assays) for which valid results were reported. For analyses using the mITT population, subjects will be grouped based on randomized study arm.

6.3.3. Per Protocol Population

The per protocol (PP) population includes all subjects in the mITT with the following exclusions:

- Data from all available visits for subjects found to be ineligible at baseline.
- Data from all visits for subjects that did not contribute venous blood samples for immunogenicity testing (HAI, NAI or Neut antibody assays) at baseline (Day 1).
- Data from all visits subsequent to major protocol deviations or events, in the opinion of the principal investigator and DMID scientific lead, expected to impact immune response such as:
 - Receipt of non-study licensed live vaccine within 30 days before or after study vaccination,
 - Receipt of non-study licensed inactivated vaccine within 14 days before or after study vaccination,
 - Receipt of immunosuppressive therapy (e.g., corticosteroids) within 30 days before or after the first study vaccination.
- Data from any visit that occurs out of window by more than one day:
 - Visit 2 data collected before Day 2 or after Day 4 post study vaccination.
 - Visit 3 data collected before Day 6 or after Day 10 post study vaccination.
 - Visit 4 data collected before Day 26 or after Day 32 post study vaccination.

- Visit 5 data collected before Day 53 or after Day 61 post study vaccination
- Visit 6 data collected before Day 75 or after Day 105 post study vaccination.
- Visit 7 data collected before Day 114 or after Day 122 post study vaccination.
- Visit 8 data collected before Day 165 or after Day 195 post study vaccination.
- Visit 9 data collected before Day 350 or after Day 401 post study vaccination.

For analyses using the PP population, subjects will be grouped based on study vaccinations received.

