
 
• To assess protocol specified AESIs, medically-attended adverse events (MAAEs), including new-onset chronic medical conditions (NOCMCs) and potentially immune-mediated medical conditions (PIMMCs) that occur after receipt of study product.
 
	
 
• Occurrence of all protocol specified AESIs, MAAEs, including NOCMCs and PIMMCs, from the time of the first study vaccination through approximately 12 months following the first vaccination.
 

Secondary Immunogenicity Objectives
	
Secondary Immunogenicity Outcome Measures

 
• To assess the HAI, Neut and NAI ELLA responses to the 2019/2020 QIV strains prior to (Day 1) and approximately 28 days after vaccination with the 2019/2020 QIV in all study groups
 
	
 
• The percentage of subjects achieving an HAI titer <math>\geq 1:40</math> against 2019/2020 QIV strains approximately on Days D90 (baseline) and D118 (28 days post-2019/2020 vaccine) for each study group.
 
• The percentages of subjects achieving HAI, Neut and NAI titer seroconversion, against 2019/2020 QIV strains on
 

	
approximately Day 118 for each study group (NAI titers will only be assessed on study groups 1,2 and 3).
 
 
• Serum Neut, HAI and NAI GMTs against 2019/2020 QIV strains approximately on Days D90 (baseline) and D118 (28 days post-2019/2020 QIV) for each study group (NAI titers will only be assessed on study groups 1,2 and 3).
 
• Ratio of serum Neut, HAI and NAI GMTs against 2019/2020 QIV strains between adjuvanted and unadjuvanted study groups approximately on Days D90 (baseline) and D118 (28 days post-2019/2020 QIV). NAI titers will only be assessed on study groups 1,2 and 3.
 
• Serum Neut, HAI and NAI GMFRs against 2019/2020 QIV strains from baseline (D90) on approximately D118 for each study group (NAI titers will only be assessed on study groups 1,2 and 3).
 

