**Table 3: Venipuncture Volumes**

Study Visit Number	V00	V01	V02	V03	V04	V05	V06	V07	V08	V09	Cumulative Blood Volume Total (mL)
Study Day post first study vaccination	Screening D-28 to -1	Enrollment Dose 1 D1	D2 +1	D8+/-1d	D29+/-2d	D57+/-3d	D90 +/-14 d	D118 +/-3 d	D180 +/- 14d	D365-14/+35d	
Study Vaccination		X					X				
ESR	4 ^										4
Clinical Safety Laboratory Evaluations	6 ^	6 #†		6							18
Serological Assays		20 †		20	20	20	20 †	20	20	20	160
Cellular Immunology Assays		80 †		48	80		48 †				256
Tempus RNA Tube		3 †	3	3							9
Per Visit Blood Volume Total (mL)	10	109	3	77	100	20	68	20	20	20	
Running Blood Volume Total (mL)	10	119	122	199	299	319	387	407	427	447	447

^ Drawn up to 28 days prior to the first study vaccination. The ESR value must be confirmed as less than 30 mm per hour prior to randomization and prior to first study vaccination. Screening WBC, Hgb, PLT, ALT, T. Bili, AST, GGT, ALP and serum lipase and serum amylase and Cr must be within the accepted ranges outlined in the inclusion criteria prior to randomization and study vaccination.

# Clinical safety laboratory evaluations collected on Day 1 prior to first study vaccination will be considered as baseline.

† Blood must be drawn immediately prior to each study vaccination.

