#### **8.2.5 Visit 06, Day 90, Clinic Visit**

##### **(Window: Day 90 +/- 14d)**

- Interim medical history, including an assessment for new medical conditions, stability of chronic diseases and symptoms suggestive of AESIs (including Protocol Specified AESIs, MAAEs, NOCMCs and PIMMCs), will be obtained by interview of subjects and any changes since the previous clinic visit will be noted.
- Receipt of any non-study influenza vaccines will be recorded on the appropriate DCF.

- SAEs, AESIs (including Protocol Specified AESIs, MAAEs, NOCMCs and PIMMCs) will be recorded on the appropriate DCF.
- A targeted physical examination performed prior to study vaccination, including an assessment for signs suggestive of AESIs (including Protocol Specified AESIs, MAAEs, NOCMCs and PIMMCs), may be performed, if indicated based on review of interim medical history, by a study clinician licensed to make medical diagnoses and listed on the Form FDA 1572 as the site PI or sub-investigator .
- Approximately 20 mL of venous blood will be collected immediately prior to study vaccination for serological assays.
- Approximately 48 mL of venous blood will be collected immediately prior to study vaccination for immunological assays.
- Subjects will then receive one 0.5 mL dose of 2019-2020 Fluzone or Flublok QIV study vaccine via a single IM injection into the deltoid muscle of the subject's preferred arm. Subjects who received 2018-2019 Fluzone QIV will receive 2019-2020 Fluzone QIV. Subjects who received 2018-2019 Flublok QIV will receive 2019-2020 Flublok QIV. The site of injection (right or left arm) and time of study vaccine administration to the subject will be recorded on the appropriate DCF. Any SAE's will be recorded on the appropriate DCF prior to discharge.

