#### **8.2.6 Visit 07, Day 118, Clinic Visit**

##### **(Window: Day 118 +/- 3d)**

- Interim medical history, including an assessment for new medical conditions, stability of chronic diseases and symptoms suggestive of AESIs (including Protocol Specified AESIs, MAAEs, NOCMCs and PIMMCs), will be obtained by interview of subjects and any changes since the previous clinic visit will be noted.
- Receipt of any non-study influenza vaccines will be recorded on the appropriate DCF.
- SAEs, AESIs (including Protocol Specified AESIs, MAAEs, NOCMCs and PIMMCs) will be recorded on the appropriate DCF.
- A targeted physical examination, including an assessment for signs suggestive of AESIs (including Protocol Specified AESIs, MAAEs, NOCMCs and PIMMCs), may be performed, if indicated based on review of interim medical history, by a study clinician

licensed to make medical diagnoses and listed on the Form FDA 1572 as the site PI or sub-investigator.

- Approximately 20 mL of venous blood will be collected for serological assays.

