8.2. Secondary Immunogenicity Analyses

The secondary immunogenicity endpoints HAI, Neut and NAI seroconversion, percentage of subjects with titer $\geq 1:40$ for HAI, GMFRs, GMTs, and ratios of GMTs (between adjuvanted group and unadjuvanted) against the 2019/2020 QIV strains 28 days after vaccination with the 2019/2020 QIV (Day 118) will be summarized as described above. HAI and Neut seroconversion, percentage of subjects with HAI titers $\geq 1:40$, GMFRs, GMTs, and ratios of GMTs for HAI and Neut against heterologous influenza A/H3 strains on approximately Days 8, 29, 57, 90, and 118 after study vaccination with the 2018/2019 QIV will be also presented. HAI, Neut and NAI seroconversion, percentage of subjects with HAI and Neut titers $\geq 1:40$, and GMTs against the 2018/2019 QIV strains on approximately Days 8, 29, 57, 90, and 118 after study vaccination will be presented. HAI, Neut, and NAI GMFRs against the 2018/2019 QIV strains on approximately Day 57 and Day 90 will also be presented. NAI seroconversion, NAI GMTs and ratios of NAI GMTs against heterologous N1 and N2 NA antigens will also be assessed on approximately Days 8, 29, 57, 90, and 118 for study groups 1, 2 and 3. No formal hypothesis testing is planned.

Secondary summaries for the 2019/2020 QIV strains are provided in [Table 69](#), [Table 70](#), [Table 71](#), [Table 72](#), [Table 73](#), [Table 74](#), [Table 75](#), [Table 76](#), [Table 77](#), [Table 78](#), [Table 79](#), and [Table 80](#). Summaries of HAI, and Neut against heterologous H3 Influenza strains for both mITT and PP populations will also be provided in [Table 81](#), [Table 82](#), [Table 83](#), [Table 84](#), [Table 85](#), [Table 86](#), [Table 87](#), [Table 88](#), [Table 89](#), and [Table 90](#) for HAI, and [Table 91](#), [Table 92](#), [Table 93](#), [Table 94](#), [Table 95](#), [Table 96](#), [Table 97](#), and [Table 98](#) for Neut. Summaries of NAI against heterologous N1 and N2 antigens will be presented in [Table 99](#), [Table 100](#), [Table 101](#), [Table 102](#), [Table 103](#), [Table 104](#), [Table 105](#), [Table 106](#), [Table 107](#), [Table 108](#), [Table 109](#), and [Table 110](#).

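### The 2019/2020-strain endpoints are set at about 28 days after dose 2, but the visit windows and per-protocol limits count from dose 1, so per-protocol samples can be 9 to 47 days after dose 2

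*SAP*

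**What the plan says.** **Endpoint timing, from dose 2.** Protocol Table 1 states the secondary objective for the 2019/2020 strains as responses "approximately 28 days after vaccination with the 2019/2020 QIV in all study groups". It places the outcomes "approximately on Days D90 (baseline) and D118 (28 days post-2019/2020 vaccine) for each study group". SAP 3.1 repeats this, and SAP 8.2 says that results "against the 2019/2020 QIV strains 28 days after vaccination with the 2019/2020 QIV (Day 118) will be summarized as described above".

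**Visit timing, from dose 1.** Protocol 8.2.5 gives Visit 6, where dose 2 is administered, as "Window: Day 90 +/- 14d". Protocol 8.2.6 gives Visit 7 as "Window: Day 118 +/- 3d". Neither heading names the reference vaccination, but the day row of Protocol Table 3 reads "Study Day post first study vaccination" and the schedule in Appendix A agrees. SAP 4.4.5 describes the dose 2 timing as the "protocol defined window of Day 90 +/- 14 days post first vaccination".

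**Per-protocol rule.** SAP 6.3.3 removes data visit by visit when the visit is more than one day out of window. Visit 6 data are kept on Days 75 to 105, and the rule for the response sample excludes "Visit 7 data collected before Day 114 or after Day 122 post study vaccination". The mITT population (SAP 6.3.2) has no visit window.

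**The concern.** One set of limits serves two kinds of endpoint. The 2018/2019-strain and heterologous endpoints at Visit 7 are timed from dose 1, and Days 114 to 122 suit them. The 2019/2020-strain endpoints at the same visit are timed from dose 2, whose own date may move by 14 days either way. Nothing in either document limits the interval from the actual dose 2 date to the Visit 7 sample. Deviation review under SAP 7.2 does not help, because a subject who met both windows has no deviation to review.

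At stake are seroconversion, GMT, GMT ratio, GMFR and the share with titer ≥1:40 against the 2019/2020 strains (SAP Tables 69 to 80). These may pool quite different times since dose 2 as the 28-day response, and for this purpose the PP rule can select the wrong samples.

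**Working it through.** **Inputs**
- Protocol windows: Visit 6, Days 76 to 104 (90 ± 14); Visit 7, Days 115 to 121 (118 ± 3).
- PP limits (SAP 6.3.3): Visit 6, Days 75 to 105; Visit 7, Days 114 to 122.
- Visit 6 blood is drawn immediately before dose 2 (Protocol Table 3 footnote and 8.2.5), so at that visit the sample day is the dose 2 day.

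**The plan's own figures reproduce.** The nominal interval is 118 − 90 = 28 days. The PP limits are the protocol windows widened by one day: 76 − 1 = 75, 104 + 1 = 105, 115 − 1 = 114, 121 + 1 = 122.

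**Range of the interval from dose 2 to the Visit 7 sample.** The minimum is the earliest Visit 7 day minus the latest Visit 6 day; the maximum is the reverse. Both days share one origin, so the numbering convention cancels.

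| Limits | Minimum | Maximum |
|---|---|---|
| Protocol windows | 115 − 104 = 11 | 121 − 76 = 45 |
| PP limits | 114 − 105 = 9 | 122 − 75 = 47 |

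For comparison, the Day 29 response is kept in PP only on Days 26 to 32, a span of 7 days.

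**A worked case.** With dose 2 on Day 100, a Day 115 sample is 115 − 100 = 15 days later and is kept. A sample exactly 28 days later falls on 100 + 28 = Day 128, beyond Day 122, and is excluded.

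**When 28 days is reachable.** An exact 28-day sample fits the protocol Visit 7 window only for doses on Days 87 to 93 (7 of the 29 permitted days). It is kept in PP only for doses on Days 86 to 94 (9 of those 29).

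**When 24 to 32 days is reachable** (28 ± 3, plus the SAP's one-day allowance).
- Protocol windows: 29 × 7 = 203 day pairs, of which 63 qualify (31%). They come only from doses on Days 83 to 97 (15 of 29 days). Only doses on Days 89 to 91 keep all seven Visit 7 days inside the interval.
- PP limits: 31 × 9 = 279 day pairs, of which 81 qualify (29%), from doses on Days 82 to 98.

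These are counts of possible days. The documents do not give the spread of second-dose dates.

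**Where 9 to 47 is not a bound.** GMFR and seroconversion need both the Visit 6 and Visit 7 samples, so the range holds for them when both visits are within limits. GMT, GMT ratio and titer ≥1:40 at Visit 7 need only that visit, and a Visit 7 result can stay in PP when dose 2 fell outside Days 75 to 105. Protocol 8.5 lets a site give dose 2 before Day 76 under a stated surveillance condition. As an illustration, a dose on Day 70 and a sample on Day 122 gives 122 − 70 = 52 days.

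**The case against.** The strongest reply is that one visit has to serve endpoints timed from both doses, so a compromise window is a legitimate choice. The affected results carry no hypothesis test, Table 1 says approximately, and the table shells label the rows by day after the first vaccination. Randomization is stratified by site and assessors are blinded, so dose 2 timing should not depend systematically on arm. All of that stands, and it limits the importance of the point. It does not make Days 114 to 122 a suitable selection rule for a response that SAP 8.2 places 28 days after dose 2.

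A reader might also infer more than the documents support:
- *That the interval is hidden.* It is not. Listings 9 to 11 give the actual study day of each sample, and the Visit 6 sample is drawn just before dose 2, so the interval can be found by subtraction for subjects dosed at Visit 6. What is missing is a summary: Table 15 groups second-vaccination dates by month, and Listing 1 carries no date.
- *That an early dose 2 makes the baseline post-dose.* SAP 3.2 fixes the 2019/2020 baseline at Day 90, but it calls that value pre-vaccination, blood must precede each vaccination, and the unscheduled visit in Protocol 8.5 provides for a serology draw. This needs clearer wording only.
- *That subjects who missed dose 2 stay in PP.* The list of deviations in SAP 6.3.3 is open, SAP 7.2 reviews treatment-schedule deviations, and Table 6 has a row for missed administration. The gap is that Table 12 names a missed first vaccination for PP Day 118 but not a missed second, and no explicit rule covers it.

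**Conclusion.** The concern holds. For the 2019/2020-strain endpoints the PP limits are anchored to the wrong dose: with both visits within limits they admit samples 9 to 47 days after dose 2 (11 to 45 under the protocol windows), and they can drop a sample taken at exactly 28 days. No planned table or analysis reports the interval or allows for it.

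The day-pair percentages should not be read as the share of subjects who will be mistimed. They weight every permitted day equally, which nothing in the documents supports, and the actual effect on titers is unknown. Nor do the documents show bias in the adjuvanted-to-unadjuvanted ratios. What is blurred is the meaning of each arm's result as a 28-day response. The endpoints are secondary or exploratory and descriptive, and the Day 29 primary endpoints are unaffected. The point should be fixed, but it does not threaten the trial's main results.

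**What to change.** Keep Days 114 to 122 for the 2018/2019-strain and heterologous endpoints. For the 2019/2020-strain endpoints:

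1. Compute actual days from dose 2 to the Visit 7 sample and report the distribution by arm, for mITT (Tables 69, 73, 77) and PP (Tables 70 to 72, 74 to 76, 78 to 80).
2. Add a supportive analysis of samples taken 24 to 32 days after dose 2. Do not exclude such a sample only because it falls outside Days 114 to 122.

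Two wording clarifications go with this. In SAP 3.2, define the 2019/2020 baseline as the last sample before dose 2. In SAP 6.3.3 and Table 12, list a second vaccination not received as a reason for exclusion from the PP Day 118 analysis of the 2019/2020 strains.

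Protocol 8.2.5 and 8.2.6 must be reconciled with the definition in Table 1. How that is done is for the sponsor to decide.

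**Cost.** SAP text, one summary and one added analysis, using vaccination and visit dates already recorded. Subjects who met both windows stay in PP. The restricted set may be much smaller, with wider confidence intervals: under the protocol windows no compliant Visit 7 day qualifies for doses on Days 76 to 82 or 98 to 104 (7 + 7 = 14 of 29 days). For the two B strains listed in both seasons, its Day 118 n may differ from the 2018/2019-strain tables.
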